#### **11.3.2 Adverse Events**

##### ***11.3.2.1 Adverse Events and Serious Adverse Events***

An AE is any untoward medical occurrence in a subject participating in a clinical trial. An AE can be any unfavorable and unintended sign, symptom, or disease temporally associated with the

use of the study medication, whether or not considered related to the study medication. AEs will be collected from the time a patient signs the ICF until 30 days after the final visit. AEs occurring prior to the start of treatment will be recorded in the eCRF and shown in listings but not in tables of AEs. Only TEAEs (ie, those AEs that begin or worsen in severity after the start of treatment) will be tabulated in the AE tables and discussed in the clinical study report.

Pre-existing, known clinically significant conditions observed at screening should be recorded as medical history. Worsening of a pre-existing condition by at least 1 grade per CTCAE version 5.0 should be recorded as an AE.

The definition of AEs also includes accidental injuries, reasons for any change in medication (drug and/or dose) other than planned titration, reasons for admission to a hospital, or reasons for surgical procedures (unless for minor elective surgery for a pre-existing condition). It also includes AEs commonly observed and AEs anticipated based on the pharmacological effect of the study medication. All new laboratory abnormalities and baseline abnormalities worsening by at least 1 CTCAE grade must be recorded as an AE when clinically significant.

A TEAE is any AE occurring after start of study medication or pre-existing medical condition that worsens in intensity after start of study medication.

AEs should be recorded as diagnoses, if available. If not available, separate sign(s) and symptom(s) are recorded. One diagnosis/symptom should be entered per record.

Note that death is not an event; however, the cause of death is. An exception is the event of sudden death of unknown cause. Note that hospitalization is not an event; however, the reason for hospitalization is. Procedures are not events; however, the reasons for conducting the procedures are. In general, only the reason for conducting the procedure will be captured as an AE. If deemed necessary by the investigator, a procedure can be captured along with the reason for conducting the procedure.

An overdose or medication error is not an AE unless it is temporally associated with an unfavorable or unintended sign or symptom.

Each AE is to be classified by the investigator as serious or non-serious. An SAE is any untoward medical occurrence or effect that occurs at any dose which:

- Results in death
- Is life-threatening (ie, an immediate risk of death)
- Requires in-patient hospitalization or prolongation of existing hospitalization
- Results in persistent or significant disability/incapacity
- Is associated with a congenital anomaly/birth defect
- Is an important medical event

An AE caused by an overdose or medication error is considered serious if a criterion listed in the definition above is fulfilled.

Important AEs that may not result in death, may not be life-threatening, or do not require hospitalization may be considered serious when, based upon appropriate medical judgment, they may jeopardize the subject's safety or may require medical or surgical intervention to prevent one of the outcomes listed above.

SAEs also include any other event that the investigator or sponsor judges to be serious or which is defined as serious by the regulatory agency.

The investigator is to report all directly observed AEs and all AEs spontaneously reported by the study patient using concise medical terminology. In addition, each study patient will be questioned about AEs. The question asked will be "Since you began taking the study medication, have you had any health problems?"

#### ***11.3.2.2 Procedures for Assessing, Recording, and Reporting Adverse Events and Serious Adverse Events***

Throughout the study, the investigator will closely monitor each patient for evidence of drug intolerance and for the development of clinical or laboratory evidence of AEs. All AEs (expected or unexpected) which occur during the course of the study, whether observed by the investigator or by the patient, and whether or not thought to be drug-related, will be reported and followed until resolution or until they become stable.

The description of the AE will include description of event, start date, stop date, intensity, if it was serious, relationship to test drug, change in test drug dosage, if the patient died, and if treatment was required.

AEs will be graded according to CTCAE version 5.0. A copy of the terminology can be found at:

[https://ctep.cancer.gov/protocoldevelopment/electronic\\_applications/docs/CTCAE\\_v5\\_Quick\\_Reference\\_8.5x11.pdf](https://ctep.cancer.gov/protocoldevelopment/electronic_applications/docs/CTCAE_v5_Quick_Reference_8.5x11.pdf)

For AEs not included in the CTCAE version 5.0, the following criteria will apply:

Grade	Description
1	Mild
2	Moderate
3	Severe
4	Life-threatening or disabling
5	Fatal

AEs will be coded, grouped, and tabulated by Medical Dictionary for Regulatory Activities (MedDRA) preferred terms (PTs) according to body system organ class (SOC). Events will be coded into 1 of the following 5 causality categories:

Category	Definition
Definitely	This category applies when, after careful medical consideration, there is almost no consideration of other causation.
Probably	There is a clinically plausible time sequence between onset of the AE and study treatment administration. The AE is unlikely to be caused by a concurrent and/or underlying illness, other drugs, or procedures. If applicable the AE follows a clinically consistent resolution pattern upon withdrawal of study drug.
Possibly	There is a clinically plausible time sequence between onset of the AE and study treatment administration, but the AE could also have been caused by the concurrent/underlying illness, other drugs, or procedures. “Possible” should be used when study treatment administration is one of several biologically plausible causes of the AE.
Unlikely	The AE is most likely due to a non-study-treatment-related cause. However, association with the study treatment cannot be completely ruled out.
Not related	Another cause of the AE is most plausible, and a clinically plausible temporal sequence is inconsistent with the onset of the AE and study treatment administration and/or a causal relationship is considered biologically implausible.

AEs with the causality assessed as unlikely and not related are categorized as not related to study medication for regulatory reporting. Investigators will assess events for relationship to study medication (BC-819) and independently to study procedures (eg, catheterization for direct visualization or administration of medicine). Investigators may assess an event as possibly related to more than 1 cause.

**All SAEs must be reported immediately (no more than 24 hours after becoming aware of the event).** The investigator must complete the initial SAE Report Form and fax/e-mail it within 24 hours according to the SAE Report Form instructions. Any SAEs occurring within 30 days following study discontinuation must also be reported. The sponsor medical monitor or delegate is responsible for providing the sponsor's assessment of causality and expectedness that will be

considered when determining if the event qualifies as a serious unexpected suspected adverse reaction (SUSAR) requiring expedited reporting to regulatory authorities.

Sponsor Medical Monitor:

[name]

E-mail: [[contact]](mailto:[contact])

## 12. STUDY PROCEDURES AND FLOWCHARTS

The administration of BC-819 is separated into 2 phases, the induction phase and the maintenance phase.

During the induction phase, eligible patients will receive BC-819 once per week for 10 consecutive weeks. The flow chart for the induction phase is [Table 12.1](#).

During the maintenance phase, patients will transition to once every 3 weeks administration of BC-819 and will be evaluated every 12 weeks by cystoscopy for staging of response in order to determine continued participation. The urine cytology and cystoscopy must be completed within 14 days prior to the next administration of BC-819 and fully evaluated before initiating the treatment. The flow charts for the maintenance phase are [Table 12.2](#) and [Table 12.3](#).

In each of the the study flow charts, a study week is defined as 7 days. A description of each procedure is in Section [12.1](#). End of study procedures are required within 4 weeks of leaving the study.

**Table 12.1 Induction Phase**

Visit	Screening	V1	V2	V3	V4	V5	V6	V7	V8	V9	V10
Day	≤42 days before V1	1	8	15	22	29	36	43	50	57	64
Baseline only procedures	X										
Interim physical examination including ECOG performance status	X	X	X	X	X	X	X	X	X	X	X
Vital signs	X	X	X	X	X	X	X	X	X	X	X
Complete blood count and biochemical profile	X										
Urine sample for urinalysis (routine and microscopic)	X										
Urine sample for culture and sensitivity	X										
Urine sample for cytology	X										
Adverse events	X	X	X	X	X	X	X	X	X	X	X
Prior and concomitant medications	X	X	X	X	X	X	X	X	X	X	X
Biopsy	X										
Cystoscopy	X										
TUR/re-TUR	X										
QOL assessment		X									
Administration of BC-819		X	X	X	X	X	X	X	X	X	X

Detailed descriptions of procedures and timing are in Section 12.1.

Abbreviations: BC-819 = recombinant DNA plasmid complexed with polyethylenimine; ECOG = Eastern Cooperative Oncology Group; QOL = quality of life; re-TUR = repeat transurethral resection; TUR = transurethral resection; V = visit.

**Table 12.2 Maintenance Treatment Through Visit 23 (Week 48)**

Visit	V11	V12	V13	V14	V15	V16	V17	V18	V19	V20	V21	V22	V23
Week	12 Day 84	15	18	21	24	27	30	33	36	39	42	45	48
Interim physical examination including ECOG performance status	X	X	X	X	X	X	X	X	X	X	X	X	X
Vital signs	X	X	X	X	X	X	X	X	X	X	X	X	X
Complete blood count and biochemical profile	X				X								X
Urine sample for urinalysis (routine and microscopic)	X				X								X
Urine sample for culture and sensitivity	X				X								X
Adverse events	X	X	X	X	X	X	X	X	X	X	X	X	X
Concomitant medications	X	X	X	X	X	X	X	X	X	X	X	X	X

**Maintenance Treatment Through Visit 23 (Week 48)**

Visit	V11	V12	V13	V14	V15	V16	V17	V18	V19	V20	V21	V22	V23
Week	12 Day 84	15	18	21	24	27	30	33	36	39	42	45	48
Mandatory response assessment for patients with CIS	X				X a				X a				X a
Urine sample for cytology (must be completed within 14 days prior to BC-819 administration)	X				X				X				X
Cystoscopy (must be completed within 14 days prior to BC-819 administration)	X				X				X				X
TUR/re-TUR/biopsy as clinically indicated	X				X				X				X
QOL assessment				X								X	
Administration of BC-819	X	X	X	X	X	X	X	X	X	X	X	X	X

aMandatory in patients who have not previously achieved a CR in their baseline CIS.

Detailed descriptions of procedures and timing are in Section 12.1.

Abbreviations: BC-819 = recombinant DNA plasmid complexed with polyethylenimine; CIS = carcinoma in situ; ECOG = Eastern Cooperative Oncology Group; QOL = quality of life; re-TUR = repeat transurethral resection; TUR = transurethral resection; V = visit.

**Table 12.3 Maintenance Treatment Through Visit 39 (Week 96)**

Visit	V24	V25	V26	V27	V28	V29	V30	V31	V32	V33	V34	V35	V36	V37	V38	V39/EOS
Week	51	54	57	60	63	66	69	72	75	78	81	84	87	90	93	96
Interim physical examination including ECOG performance status	X	X	X	X	X	X	X	X	X	X	X	X	X	X	X	X
Vital signs	X	X	X	X	X	X	X	X	X	X	X	X	X	X	X	X
Complete blood count and biochemical profile								X								X
Urine sample for urinalysis (routine and microscopic)								X								X
Urine sample for culture and sensitivity								X								X
Adverse events	X	X	X	X	X	X	X	X	X	X	X	X	X	X	X	X
Concomitant medications	X	X	X	X	X	X	X	X	X	X	X	X	X	X	X	X
Urine sample for cytology (must be completed within 14 days prior to BC-819 administration)				X				X				X				X
Cystoscopy (must be completed within 14 days prior to BC-819 administration)				X				X				X				X
TUR/re-TUR/biopsy as clinically indicated				X				X				X				X
Administration of BC-819	X	X	X	X	X	X	X	X	X	X	X	X	X	X	X	

Detailed descriptions of procedures and timing are in Section 12.1.

Abbreviations: BC-819 = recombinant DNA plasmid complexed with polyethylenimine; ECOG = Eastern Cooperative Oncology Group; EOS = end of study; re-TUR = repeat transurethral resection; TUR = transurethral resection; V = visit.

## 12.1 Description of Study Procedures

The following procedures will be performed at the times noted in [Table 12.1](#), [Table 12.2](#), and [Table 12.3](#).

Baseline tests for evaluating eligibility will include the following:

**Informed consent:** All patients must sign the ICF. Consent by a guardian is not acceptable unless the patient is unable to sign because of a physical problem with a hand or arm. In that case, the patient must give verbal consent, which must be witnessed by an observer not directly involved in the study. Patients who are not mentally competent to consent on their own are not permitted to participate in the study. The consent process must be properly documented in the source data.

**Medical History and Physical Examination:** Full medical history, including details of bladder cancer diagnosis, treatment and course, and physical examination during screening; directed physical examination of pertinent systems and interim history at other visits. Patients will be weighed at screening, at the start of maintenance therapy visit, and at EOS; weight is to be recorded in kilograms. Height will be collected only at baseline physical examination.

**Electrocardiogram:** a 12-lead electrocardiogram (ECG) will be performed at baseline for patients with a history or symptoms of cardiac or respiratory abnormality 12-lead if not performed within 1 month of study entry. Results from an ECG performed before study entry must be available for review by the investigator or his/her designee; a report alone is not adequate.

**Chest X-Ray:** Posterior-anterior and lateral chest x-ray, will be performed at baseline if not performed within 6 months before study entry. Results from a chest x-ray performed before study entry must be available for review by the investigator or his/her designee; a report alone is not adequate.

**Urine Pregnancy Test:** For women of childbearing potential only. Women who are at least 3 months past surgical sterilization and those with no menstruation for at least 12 months prior to entering the study are no longer considered to be of childbearing potential.

**Interim Physical Examination:** Examination of pertinent systems (ie, abdomen, back, and systems about which patient notes symptoms currently or at previous visit). Weight is to be recorded in kilograms at the start of maintenance therapy visit and at EOS.

In conjunction with the physical examination, ECOG performance status will be collected at screening and at each study visit.

**Table 12.4    Eastern Cooperative Oncology Group Performance Status: Scored 0 (Normal Function) through 5 (Dead)**

ECOG PERFORMANCE STATUS a	
Grade	ECOG
0	Fully active, able to carry on all pre-disease performance without restriction
1	Restricted in physically strenuous activity but ambulatory and able to carry out work of a light or sedentary nature, eg, light housework, office work
2	Ambulatory and capable of all self-care but unable to carry out any work activities. Up and about more than 50% of waking hours
3	Capable of only limited self-care, confined to bed or chair more than 50% of waking hours
4	Completely disabled. Cannot carry on any self-care. Totally confined to bed or chair

a Oken et al. 1982.

**Vital Signs:** Pulse, respiratory rate, systolic and diastolic blood pressure, and temperature (in °C) will be recorded at all visits. At treatment visits, vital signs should be recorded within 30 minutes prior to starting treatment.

**Complete Blood Count/Biochemical Profile:** Complete blood count includes hemoglobin, total red cell count, total white blood cell (WBC) count, absolute values for individual WBC types, and platelet count.

Biochemical profile will include, at a minimum, albumin, alkaline phosphatase, alanine aminotransferase, aspartate aminotransferase, bicarbonate, (total) bilirubin, blood urea nitrogen, calcium, chloride, creatinine, glucose, potassium, sodium, and total protein.

**Urinalysis:** At visit indicated, urinalysis will include the following:

Routine: blood, leukocytes, glucose, ketones, nitrites, pH, protein, and specific gravity

Microscopic: WBC, red blood cells, bacteria, epithelial cells, crystals (with type identified), and mucus

**Urine for Culture and Sensitivity:** A urine sample will be collected for culture and sensitivity analysis at each visit indicated.

**Urine cytology:** The urine sample for cytology testing should be collected and analysed within 14 days prior to scheduled treatment administration.

**Adverse Events:** Patients will be questioned regarding the occurrence or resolution of AEs. Details regarding collection and assessment of AEs are given in Section 11.3.2 of this protocol.

**Prior and concomitant medications:** At baseline, a complete history of all treatment for bladder cancer, as well as all medications (both prescription and over the counter) should be recorded, including medication prescribed and over the counter and taken within 30 days before the screening visit, which will be recorded in the eCRF. During the study, all medications, both prescription and over the counter, are to be recorded in the eCRF. Indications for each medication should be collected, including whether the medication was taken prophylactically or therapeutically. Complete dosing information (dosage and actual number of doses taken each day) for all medications taken during the study are to be recorded.

**Biopsy:** Biopsy is required at baseline. Otherwise, biopsy is only needed if either cystoscopy or cytology result is positive. At baseline, site-directed mapping biopsies of normal appearing mucosa and any suspicious flat or papillary lesions must be performed. A sample of the resected tumors should be made available for local pathology review and study documentation.

**Cystoscopy:** Cystoscopy will be performed at the predetermined visits as indicated in the study schedules ([Table 12.1](#), [Table 12.2](#), and [Table 12.3](#)) with a consistent imaging technique when possible. Enhanced imaging (eg, blue-light or narrow band) is preferred when available. Cystoscopy should be performed within 14 days prior to scheduled treatment administration.

All interior surfaces of the bladder will be examined systematically, and observations will be recorded. Any suspicious lesions viewed during cystoscopy should be clearly indicated on a bladder diagram attached to the source document and numbered. Any biopsy specimens taken during cystoscopy should be immediately fixed in formalin, identified by patient's name, identification code, specimen number, and date (in accordance with the number assigned on the bladder diagram) and submitted for histopathology processing and evaluation at the local hospital pathology laboratory.

A complete description of visual findings must be documented in the eCRF. Should recurrent papillary tumors (of any stage or grade) or new CIS lesions be visualized in cystoscopy, a re-TUR procedure is indicated to resect all visible papillary tumors and fulgurate all CIS lesions that did not clear when indicated. All resected specimens are to be examined for exclusion of T2 or muscle invasive disease.

**Transurethral Resection:** Transurethral resection or repeat of previous TUR should be done as indicated in the study schedules by direct visualization.

**Quality of Life Questionnaires** Quality of life will be assessed via the EORTC QLQ-C30 (a general questionnaire for cancer) and the QLQ-NMIBC24 (a specific questionnaire for NMIBC disease) for all patients according to the study procedures flow charts ([Table 12.1](#), [Table 12.2](#), and [Table 12.3](#)). The results will be recorded in the eCRF.

**Administration of BC-819:** Study treatment will be administered as described in Section [9.4](#) of the protocol. The window for treatment administration should be  $\pm$  5 days during induction and  $\pm$  1 week during maintenance. However, treatment is not to be more frequent than every 5 days at any time during study.

## 13. STATISTICAL METHODS PLANNED AND SAMPLE SIZE

### 13.1 Determination of Sample Size

The primary endpoint of the study will be based on patients in the full analysis set (FAS) population. The primary endpoint will be analyzed using a two-sided 95% CI for the CR rate in patients who have CIS at baseline (with or without papillary disease). A total of 140 treated patients will be included in this study, and it is estimated that between 70 and 100 of these will have CIS. Assuming at least 70 patients with CIS, this sample size will provide over 95% power to detect a difference in CR rate in CIS patients of 20% and an alternative hypothesis rate of 40% using an exact binomial test with a nominal 0.05 two-sided significance level. If 100 CIS patients are treated, the power will be approximately 92% to detect a difference from 20% using an alternative hypothesis rate of 35%. The power is higher to detect differences from rates lower than 20%.

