During the study, patients will undergo repeat direct visualization (ie, cystoscopy  $\pm$  biopsy and cytology) and repeat TUR (as needed for cause) every 12 weeks during the first and second year. Patients with persistent CIS which does not resolve by the 12-week assessment, or at subsequent 12-week assessments, or who have recurrence or new evidence of CIS or high-grade papillary disease at any time will be discontinued and classified as nonresponders and recurrences in the primary and secondary endpoint analyses. Patients benefiting from treatment, with no documented high-grade recurrence or progression, will continue to receive maintenance therapy every 3 weeks. Appearance or persistence of lower grade tumors will not be considered as recurrence for the primary and secondary endpoint analyses, and patients with only low-grade tumors should continue treatment after resection and histological confirmation.

**NUMBER OF PATIENTS (PLANNED):** It is planned to enroll and treat 140 patients (N=140), of which 70 to 100 are estimated to have CIS (with or without papillary disease). Assuming at least 70 patients with CIS, this sample size will provide over 95% power to detect a difference between CR rate in CIS patients of 20% and an alternative hypothesis proportion of 40% using an exact binomial test with a nominal 0.05 two-sided significance level. If 100 CIS patients are enrolled, the power will be approximately 92% to detect a difference from 20% assuming an alternative hypothesis proportion of 35%. The power is higher to detect a difference from CR rates lower than 20%.

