**STATISTICAL ANALYSIS:**

Analyses will generally be performed for the entire patient population, subgroups of patients with papillary lesions only, and patients with CIS (with or without papillary lesions). Determination of success for the treatment will be based on the full analysis set population of all treated patients. The primary endpoint will be analysed using a two-sided 95% binomial exact CI (Clopper-Pearson) for the rate of patients with baseline CIS who have a complete response.

Duration of response in CIS patients who have a complete response will be calculated using Kaplan-Meier methods starting from the documented onset of the complete response to the assessment where the patient no longer meets the definition of complete response..

In addition to time point analyses of rates of freedom from recurrence, Kaplan-Meier plots of recurrence-free survival will be calculated for all patients. Kaplan-Meier methods will also be used to estimate progression-free survival and overall survival rates at 48, 72, and 96 weeks.

The first 35 patients enrolled are to have CIS (with or without papillary disease). An interim futility analysis will be performed on these patients and if 9 or fewer of these patients have complete responses the study may be discontinued. Once the first 35 patients with CIS are enrolled and 10 or more complete responses are documented, enrollment may continue with the full study population (including patients with high-grade papillary disease without CIS who meet inclusion and exclusion criteria).

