#### **13.5.2 Interim Analyses**

The first 35 patients in the study are to be CIS patients (with or without papillary disease). An interim analysis for futility will be conducted using the response data in these patients. If 9 or fewer of these first 35 patients achieve CR, the study may be stopped for futility. If 10 or more

patients achieve a CR, then the study will continue and all patients meeting entry criteria may be enrolled (including those with papillary disease without CIS). The enrollment will be paused after 35 patients to evaluate this data unless 10 or more responses have already been documented when the 35th CIS patient is enrolled.

When the true CR rate is 40% or higher, the probability of proceeding with 10 or more CRs out of the first 35 patients is over 94%. When the true CR rate is 15% or lower, the probability of 9 or fewer responses is over 97%.

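### The stated power figures are for a single-stage test and leave out the futility look at 35 CIS patients; if that non-binding stop is followed, power is about 91% (70 CIS, 40%) and about 80% (100 CIS, 35%).

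*Protocol*

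**What the plan says.** **Power.** Protocol 13.1 bases the sample size on the CR rate in CIS patients. It compares a reference rate of 20% with 40% ("difference in CR rate in CIS patients of 20% and an alternative hypothesis rate of 40" percent), "using an exact binomial test with a nominal 0.05 two-sided significance level". The claim at the low end of the expected CIS count, at least 70 patients, is: "this sample size will provide over 95% power to detect a difference in CR rate in CIS patients of 20" percent. At the high end: "If 100 CIS patients are treated, the power will be approximately 92% to detect a difference from 20" percent, with a 35% alternative. The Synopsis (number of patients planned) has the same claim as "this sample size will provide over 95% power to detect a difference between CR rate in CIS patients of 20" percent, and SAP 7.1.5 repeats it.

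**Analysis.** The Synopsis names the matching interval: "The primary endpoint will be analysed using a two-sided 95% binomial exact CI (Clopper-Pearson").

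**Futility look.** Protocol 13.5.2 and SAP 7.5 add a look at the first 35 patients, all with CIS: "If 9 or fewer of these first 35 patients achieve CR, the study may be stopped for futility". With 10 or more CRs the study goes on and opens to papillary-only patients. Both sections give two operating characteristics: over 94% chance of reaching 10 CRs at a true rate of 40%, and over 97% chance of 9 or fewer at 15%. Neither gives a figure at 35%.

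No section gives power with the look included, and none says that the stated power leaves it out.

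**The concern.** A trial with a futility stop can succeed only if it passes the look and then reaches the final cut-off. Its overall power is therefore lower than that of a single test on the full sample, and cannot exceed the chance of passing the look if the stop is followed. The plan puts that chance at over 94% for a 40% CR rate but states power of over 95% at the same rate. With the rule applied, the two statements do not fit together.

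The 35% alternative matters more. It is one of the two rates for which the plan states power, but the interim sections do not cover it. A reader of Protocol 13.1 would put the risk of missing a true 35% rate at about 8%. Protocol 7.5 presents the study as possible primary evidence for a marketing application, so the stated chance of success should describe the design as it may be run.

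**Working it through.** **Inputs.** Reference rate 20%, alternatives 40% (n = 70) and 35% (n = 100), exact two-sided 0.05 test: Protocol 13.1. Clopper-Pearson interval: Synopsis, statistical analysis. Look at 35 CIS patients, continue with 10 or more CRs: Protocol 13.5.2 and SAP 7.5.

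**Step 1: cut-offs.** Success means that the lower Clopper-Pearson limit exceeds 20%. This is the smallest r with P(X ≥ r | n, 0.20) ≤ 0.025.

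- n = 70: P(X ≥ 21) = 0.0303 and P(X ≥ 22) = 0.0159, so r = 22. The lower limit is 20.9% at 22 CRs and 19.6% at 21.
- n = 100: P(X ≥ 28) = 0.0342 and P(X ≥ 29) = 0.0200, so r = 29. The lower limit is 20.4% at 29 CRs and 19.5% at 28.

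**Step 2: the plan's own figures, single stage.**

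- P(X ≥ 22 | 70, 0.40) = 0.9454. Stated: over 95%.
- P(X ≥ 29 | 100, 0.35) = 0.9152. Stated: about 92%.

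The second figure reproduces. The first falls about half a point short. A two-sided exact test that orders outcomes by likelihood gives the same cut-offs and powers. A normal approximation (96.5%) or a one-sided 0.05 exact test (96.8%) would exceed 95% at n = 70, but neither is the stated test. So the stated powers are single-stage values.

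**Step 3: the interim figures.**

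- P(X ≥ 10 | 35, 0.40) = 0.9425, matching over 94%.
- P(X ≤ 9 | 35, 0.15) = 0.9708, matching over 97%.
- Not in the plan: P(X ≥ 10 | 35, 0.35) = 0.8349, so P(X ≤ 9) = 0.1651.

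**Step 4: power with the stop followed.** Let X₁ be the CRs in the first 35 and X₂ those in the remaining n − 35:

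Power = Σ (x = 10 to 35) P(X₁ = x | 35, p) × P(X₂ ≥ r − x | n − 35, p)

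| CIS patients | True CR rate | Stated | Single stage | Pass the look | Power, stop followed |
|---|---|---|---|---|---|
| 70 | 40% | over 95% | 94.5% | 94.2% | 91.1% |
| 100 | 35% | about 92% | 91.5% | 83.5% | 79.7% |

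Against the single-stage values the loss is 94.5 − 91.1 = 3.4 points and 91.5 − 79.7 = 11.8 points. At 35% the chance of a missed effect is 100 − 79.7 = 20.3%. Failing the look accounts for 16.5 points of that, and failing the final test after passing it accounts for the other 3.8.

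**Step 5: type I error.** The same sum at p = 0.20 gives an upper-tail error of 0.0132 (n = 70) and 0.0136 (n = 100), below the single-stage 0.0159 and 0.0200. The stop does not inflate it.

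**The case against.** **The stop is discretionary.** Protocol 13.5.2 and SAP 7.5 say the study *may* be stopped, and the Synopsis that it *may* be discontinued. In the design sections, 10 documented responders are the condition for admitting papillary-only patients. A reader might infer that over 95% is impossible under the plan, or that the design delivers 91% and 80% outright. The documents do not support that. The 94.2% is a ceiling only if the sponsor always stops. Depending on how the discretion is used, power lies between 91.1% and 94.5% at n = 70, and between 79.7% and 91.5% at n = 100. This part of the objection stands. It does not rescue the text, because no section says that the stated power assumes the stop is ignored, and the interim sections themselves treat 10 or more CRs as the event of proceeding.

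**The interim risk is partly disclosed.** At 40% a reader can see a stopping risk of about 6%. That is true, but nothing shows the 35% case or the combined power.

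**The 70-patient shortfall is small.** The claim is for at least 70. From 70 to 100 CIS patients, single-stage power at 40% is below 95% only at 70 (94.5%) and 73 (94.7%), because of the discreteness of the exact test. This is fair; the half point is a correction of detail.

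**The CIS count.** A reader might also infer that power will be lower still because no minimum number of CIS patients is enforced after the look. The plan openly states at least 70 as an assumption and estimates 70 to 100. It gives no basis for any smaller share, so no such loss is claimed here.

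**Conclusion.** The point holds in conditional form. The stated powers are single-stage figures that leave out the futility look. The exact single-stage values are 94.5% and 91.5%. If the stop is followed, they become 91.1% and 79.7%; if it is always overridden, they stay as they are. With the rule followed, over 95% power at 40% conflicts with the plan's own figure for proceeding. The larger consequence is at 35%, where the risk of missing the effect is about 20% instead of about 8%.

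The calculation assumes exactly 70 or 100 CIS patients, independent responses at one common rate, and the same CR status for the first 35 at the look as at the final analysis. If some of their later CRs were not yet counted at the look, power would be lower.

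The primary analysis, the success cut-offs and type I error control are unaffected. The error lies in the stated chance of success.

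**What to change.** In Protocol 13.1, the Synopsis and SAP 7.1.5:

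- correct the single-stage power for 70 CIS patients at 40% to about 94.5%;
- state power with the futility rule applied: about 91% (70 CIS, 40%) and about 80% (100 CIS, 35%);
- label any single-stage figure that is kept as conditional on no futility stop.

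In Protocol 13.5.2 and SAP 7.5, add the chance of 9 or fewer CRs among the first 35 at a true rate of 35% (16.5%), beside the figures at 40% and 15%.

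The cost is wording in two documents and a less favourable stated figure. The sample size, the interim rule and the analysis need no change for this correction.
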